5.2 Dose Modifying Toxicities (DMT)

Toxicities will be graded according to CTCAE version 5.0 of the NCI Common Terminology Criteria for Adverse Events. CTCAE version 5.00 is identified and located on the CTEP website at http://ctep.cancer.gov/protocolDevelopment/electronic_applications/ctc.htm. All appropriate treatment areas should have access to a copy of CTCAE version 5.0.

DMT will be defined as any of the events listed in this section that are at least possibly related to the investigational agent that occur regardless of expectedness. Please consult Table 7 for appropriate dose modifications.

- 5.2.1 The following are Dose-Modifying Toxicities (DMT's)
 - Any selumetinib-related adverse event that results in a delay of treatment > 7 days
 - Non-hematologic dose modifying toxicity is defined as:
 - o Any grade 4 non hematologic toxicity
 - o Any grade 3 non-hematologic toxicity with the exception of:
 - Grade 3 nausea and vomiting of < 3 days
 - Grade 3 asymptomatic elevation of transaminases that returns to levels meeting eligibility criteria within 7 days of study drug interruption and does not recur upon restarting drug
 - Grade 3 fever or infection if fewer than 3 days in duration
 - Grade 3 asymptomatic hypophosphatemia, hypokalemia, hypocalcemia or hypomagnesemia responsive to oral supplementation

- Grade 3 asymptomatic elevation of CPK
- Any grade 2 non-hematological toxicity that persists for more than 7 days and is considered sufficiently medically significant or sufficiently intolerable by patients as to warrant treatment interruption and/or dose reduction will be considered dose-modifying.
- Hematologic dose modifying toxicity is defined as:
 - o Any grade 4 hematologic toxicity with the exception of lymphopenia
 - o Grade 3 thrombocytopenia with bleeding

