	Grade 2 that persists for >7 days and is considered sufficiently medically significant or intolerable by patients as to warrant treatment interruption and /or dose modifying	Hold selumetinib until < grade 2, then reduce 1 dose level and resume treatment.
	Grade 3 or 4	Hold selumetinib until < grade 1, then reduce 1 dose level and resume treatment.

[figure not shown]

Version 3.0 12-Sept-2013

Cardiac Function: Please see algorithm below

Management of Asymptomatic Left Ventricular Ejection Fraction (LVEF) Reduction

* Muscular weakness, pain or tenderness

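### Table 7 orders a dose reduction for three kinds of grade 3 event that Section 5.2.1 says are not dose-modifying (minor)

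*Combined protocol and SAP*

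**What the plan says.** Section 5.2 sets the term: "DMT will be defined as any of the events listed in this section that are at least possibly related to the investigational agent". It then sends the reader on: "Please consult Table 7 for appropriate dose modifications". In Section 5.2.1 the rule for grade 3 events reads "Any grade 3 non-hematologic toxicity with the exception of", followed by five exceptions. Three of them matter here:

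- "Grade 3 nausea and vomiting of < 3 days"
- "Grade 3 fever or infection if fewer than 3 days in duration"
- "Grade 3 asymptomatic hypophosphatemia, hypokalemia, hypocalcemia or hypomagnesemia responsive to oral supplementation"

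The other two are a transient asymptomatic transaminase rise and an asymptomatic CPK rise. Section 5.2.1 also has a separate rule on delay: "Any selumetinib-related adverse event that results in a delay of treatment > 7 days" is dose-modifying.

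In Section 6.2, Table 7 has a residual row for other non-hematologic toxicity. At grade 3 or 4 its only instruction is "Hold selumetinib until < grade 1, then reduce 1 dose level and resume treatment". Section 6.2.1 permits one step down, to dose level -1, and a patient who needs to go lower leaves treatment.

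**The concern.** A grade 3 vomiting episode lasting two days is not dose-modifying under Section 5.2.1, yet it meets the residual row of Table 7, which calls for a hold and a lower dose. The same holds for the short fever or infection and for the correctable electrolyte change. No sentence in the protocol says which text prevails.

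What is at stake is the patient's dose. Only one reduction exists, so using it on an exempt event leaves no room if a qualifying toxicity follows. Stratum 1 is judged on hearing response at 24 weeks and stratum 2 on sustained tumor response, so dose intensity should follow the rule the authors intended.

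**Working it through.** The protocol gives no figure to reproduce. The check sets the two texts side by side, then sizes one reduction.

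**Step 1. Trace each grade 3 exception in Section 5.2.1.**

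| Exception | Row of Table 7 it falls in | Handled elsewhere? |
|---|---|---|
| Nausea/vomiting under 3 days | Other non-hematologic, grade 3 or 4 | No |
| Transient transaminase rise | Liver function, grade 3: restart at the same dose if recovered within 7 days | Yes, in the table |
| Fever or infection under 3 days | Other non-hematologic, grade 3 or 4 | No |
| Correctable low electrolytes | Other non-hematologic, grade 3 or 4 | No |
| Asymptomatic CPK rise | No row of its own | Yes, study calendar footnote: no reduction needed |

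Count: 5 listed, minus 1 (liver row), minus 1 (CPK footnote) = 3 left in conflict. Grade 4 raises no conflict, because Section 5.2.1 treats every grade 4 non-hematologic event as dose-modifying.

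**Step 2. Is Table 7 reached only by dose-modifying events?** If it were, the three events would never get to the row. But the table also gives actions for events that are not dose-modifying:

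- grade 1 or 2 events: keep the dose;
- hematologic grade 1 to 3, apart from thrombocytopenia with bleeding: keep the dose;
- grade 3 liver values that recover within 7 days: hold, then restart at the same dose.

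The opening paragraph of Section 5 also points directly to Section 6.2 for dose modifications, without going through 5.2. So a reader can enter the table without first applying the exceptions.

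**Step 3. Does the table look complete?** It carries four other qualifiers from Section 5.2.1, at least in substance: transaminase recovery within 7 days, grade 2 lasting more than 7 days, grade 3 thrombocytopenia with bleeding, and the exclusion of lymphopenia. It leaves out the three above.

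**Step 4. Size of one reduction (Appendix D).** Relative cut = (level 0 daily total minus level -1 daily total) / level 0 daily total, with each total being the morning plus the evening dose.

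| BSA band (m²) | Level 0 (mg/day) | Level -1 (mg/day) | Cut |
|---|---|---|---|
| 0.55–0.69 | 20 | 10 | 50% |
| 0.70–0.89 | 40 | 30 | 25% |
| 0.90–1.09 | 50 | 35 | 30% |
| 1.10–1.29 | 60 | 45 | 25% |
| 1.30–1.49 | 70 | 50 | 28.6% |
| 1.50–1.69 | 80 | 60 | 25% |
| 1.70–1.89 | 90 | 65 | 27.8% |
| 1.90 and above | 100 | 70 | 30% |

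These cuts describe any single reduction in this trial. They do not measure the effect of this wording.

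**Step 5. Frequency.** This cannot be computed. Section 7 lists nausea and vomiting at 20% or more of patients and pyrexia at 3% to below 20%, but gives no grade 3 rates. Its expected-event table lists neither infection nor any of the four low-electrolyte events.

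**The case against.** The strongest reply is that the two sections work in sequence: 5.2.1 decides whether an event is dose-modifying, and only then does Table 7 supply the action. Much supports this. Section 5.2 contains the attribution test and the delay rule, and the table has neither, so the table was not written to stand alone. Section 5.3 (starting the next course) and Section 5.6.1 (leaving treatment) both rely on the 5.2.1 concept. The CPK footnote shows that an exception there means no reduction. If the table overrode 5.2.1, the three exceptions would have no effect on dosing. The liver row is also a loose paraphrase: it drops the asymptomatic and non-recurrence conditions and adds bilirubin. Omission from the table is therefore weak evidence of intent to override.

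This stands as an account of what the authors most likely meant. It does not remove the conflict on the page, because the table itself gives actions for events outside the definition and is also reached directly from Section 5.

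The safeguards stand too. Sections 6.1 and 6.2.1 require the study chair or co-chair to be notified before any dose change, Section 12.4 provides for real-time review of dose modifying toxicities, and there is one institution.

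A reader might infer that a single short fever or vomiting episode could end a patient's treatment. The documents do not support that: even on the literal table, leaving treatment for this reason takes two reduction-triggering events, since the first only moves the patient to level -1.

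**Conclusion.** The point holds as a minor internal inconsistency in the dosing rules. For three kinds of grade 3 event, Table 7 as written orders a reduction that Section 5.2.1 does not call for, and it would use up the only reduction allowed. Misapplication is unlikely given the notification and review rules, and its frequency is unknown.

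Two stronger readings should be resisted. One is that the authors meant Table 7 to override Section 5.2.1; the evidence above points the other way. The other is that the 25% to 50% dose cuts, or some distortion of the trial's error rates, are the size of this problem. The cuts belong to any reduction, and the primary endpoints, the two-stage decision rule and the type I error do not depend on this row.

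The conclusion assumes that the figures not reproduced near Table 7 and in Section 6.1 do not restate the three exceptions. The text around Table 7 ties its figures to LVEF and muscle or CK management; the one in Section 6.1 has no identifying text.

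**What to change.** In Table 7, change the grade label of the residual row to: *Grade 3 (except events listed as exceptions in Section 5.2.1, which do not require a dose reduction) or Grade 4*. Leave the action text unchanged.

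A bare exception is better than new hold-and-resume wording. Section 5.2.1 gives no general hold instruction for these three events, and the electrolyte exception has no recovery time to refer to. An event that goes beyond its exception (3 days or more, symptomatic, or not responsive to oral supplements) stays under the row as it is. The rule on delays over 7 days also stays in force.

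The cost is one clause in one row, which can go into the next protocol amendment. For a team that already applies 5.2.1 first, practice does not change.

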5.3 Criteria for starting subsequent courses

A course may be repeated every 28 days if the patient has at least stable disease and the patient meets the following criteria within seven days of the start of each course:

- ANC $\geq 1,000/\mu L$
- Platelets $\geq 100,000/\mu L$
- Non-hematologic dose modifying toxicity related to selumetinib recovered to < grade 2 or baseline (for rash or diarrhea: tolerable grade 2 or baseline)
- No evidence of progressive disease

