5.5 Duration of Therapy

In the absence of treatment delays due to adverse event(s) or disease progression, treatment may continue for 26 courses (approximately two years) or until one of the Off Treatment Criteria found

in Section 5.6 applies.

During the second year of treatment, procedures consistent with good clinical care will continue. Patients will be seen monthly for medical history, physical exam (including height, weight, vital signs, and performance status), neurologic exam, dates of drug administration, relevant laboratory evaluations and routine neuro-imaging assessments. Therapy-related events will be recorded per standard assessments, including adverse events, date of disease progression, date of last follow up, date patient goes off treatment and date off study. Please review the table in Section 10 of the protocol for the required assessments and intervals. All patients must discontinue treatment with selumetinib following the completion of 26 courses of treatment.

5.6 **Duration of Follow Up**

Discontinuation of Treatment

At the discontinuation of treatment, the "Off Treatment Date" is to be recorded in the CRF and is to be consistent with the reason given for going off treatment. The "Last Treatment Date" is defined as the last date that the patient received protocol based therapy. Date of "off treatment" must be the greatest of the date of last treatment, date of procedure, date of patient assessment, notification of patient/family decision, or decision made by the physician that resulted in the patient being taken off protocol treatment. The reason for discontinuation of treatment must be documented by the attending investigator in the medical record and recorded in the CRF. The "Off Treatment Date" and the "Last Treatment Date" should be the same for patients that complete all protocol defined treatment.

Patients will be considered Off Treatment for the following reasons:

- 5.6.1 Development of unacceptable toxicity as outlined in Section 5.2.1 that does not resolve within 14 days.
- 5.6.2 Non-compliance with study guidelines
- 5.6.3 Progressive disease, as outlined in section 11.1 and 11.2
- 5.6.4 Development of a medical or psychiatric illness, that in the investigator's judgment renders the patient incapable of further therapy on this protocol
- 5.6.5 The patient, parent or legal guardian refuses further treatment on this protocol
- 5.6.6 Pregnancy
- 5.6.7 Completion of maximum number of courses of treatment with selumetinib

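### After a grade 3 or 4 event in the 'Other non-hematological toxicity' row, Table 7 and Section 5.3 set different recovery levels, and Section 5.6.1 does not say what counts as resolved

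*Combined protocol and SAP*

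**What the plan says.** Four places bear on restarting after a non-hematologic event.

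- Section 5.2.1 defines dose-modifying toxicity. It includes "Any grade 4 non hematologic toxicity" and "Any grade 3 non-hematologic toxicity with the exception of" a short list. Section 5.2 sends these events on: "Please consult Table 7 for appropriate dose modifications".
- Table 7 (Section 6.2), row 'Other non-hematological toxicity', grade 3 or 4: "Hold selumetinib until < grade 1, then reduce 1 dose level and resume treatment". Baseline is not mentioned. The line above it, for persistent grade 2 events, uses below grade 2 instead.
- Section 5.3 allows the next course if "the patient meets the following criteria within seven days of the start of each course". One criterion is "Non-hematologic dose modifying toxicity related to selumetinib recovered to < grade 2 or baseline", with a separate allowance, "for rash or diarrhea: tolerable grade 2 or baseline".
- Section 5.6.1 lists as a reason for ending treatment: "Development of unacceptable toxicity as outlined in Section 5.2.1 that does not resolve within 14 days". It attaches no grade to 'resolve'.

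**The concern.** The same event can fall under both recovery rules. Section 5.2.1 makes it dose-modifying, which brings in the criterion in 5.3, and Section 5.2 also refers it to Table 7. Under Section 5.1 dosing is continuous, with each four-week course following directly on the last, so a hold can easily meet the start of a course. One rule may then allow dosing while the other keeps the drug on hold.

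The 14-day limit in 5.6.1 adds to the difficulty. If 'resolve' means reaching the Table 7 level, a patient whom 5.3 regards as recovered reaches an off-treatment criterion. If it means the 5.3 level, the patient does not. What is at stake is consistent handling of treatment continuation, which is a safety matter and also determines how much treatment a patient receives before assessment.

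**Working it through.** The plan gives no figure to reproduce here, so the check sets the two rules against each other.

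**Inputs.** Let b be the baseline grade and r the residual grade after the event, each from 0 to 3, with r not below b.

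- Table 7 as printed: resume if r < 1.
- Table 7 if the sign was meant as less than or equal: resume if r ≤ 1.
- Section 5.3 (not rash or diarrhea): start the course if r < 2 or r = b.

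**All ten combinations.**

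| b | r | Table 7, r < 1 | Table 7, r ≤ 1 | Section 5.3 |
|---|---|---|---|---|
| 0 | 0 | yes | yes | yes |
| 0 | 1 | no | yes | yes |
| 0 | 2 | no | no | no |
| 0 | 3 | no | no | no |
| 1 | 1 | no | yes | yes |
| 1 | 2 | no | no | no |
| 1 | 3 | no | no | no |
| 2 | 2 | no | no | yes |
| 2 | 3 | no | no | no |
| 3 | 3 | no | no | yes |

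**Result as printed.** The rules disagree at (0,1), (1,1), (2,2) and (3,3). In each case 5.3 allows the course and Table 7 keeps the drug on hold.

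**Result with the other sign.** On whole grades, r ≤ 1 is the same as r < 2, so (0,1) and (1,1) drop out. The pairs (2,2) and (3,3) remain, because only 5.3 has a baseline allowance. The (3,3) case can arise only from a grade 4 event.

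These are combinations of grades, not patients. The counts say nothing about how often each occurs.

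**Can both rules apply at once?** Assume that course days run by the calendar during a hold, which the plan does not state. A hold that begins in the second half of a 28-day course and lasts the full 14 days then reaches or passes the start of the next course, so both rules are live.

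**Scope.** Skin, diarrhea, visual and liver events have their own rows in Table 7 and are outside this point. Asymptomatic LVEF reduction, dyspnoea and CPK elevation have algorithms in figures that are not visible in the text, so nothing is claimed about them. Grade 3 events excepted in 5.2.1 are not dose-modifying, so the 5.3 criterion does not reach them.

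**The case against.** **The sign may be unreliable.** This objection has weight. The diarrhea row of Table 7 is garbled in the available text. Section 5.4.3 has a strict sign before tolerable grade 2, where the skin row of Table 7 has less than or equal. Section 2.2.2 counts 18 of 56 patients with a related event above grade 3, yet reports only one grade 4 event, which suggests a lost 'or equal'. Against this, the less-than-or-equal sign does survive in the skin row. The question cannot be settled from the text, which is why both readings are worked through.

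**The rules may be complementary.** Table 7 could be a tiered rule for lifting a hold and 5.3 a separate check before each course, with the stricter deciding. Sections 5 and 5.2 do point to Section 6.2 and Table 7 for dose modification. That is a sensible reading, but neither pointer says that Table 7 overrides 5.3 when a course is due.

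**There is central oversight.** This is a single-institution trial, and Sections 6.1 and 6.2.1 require the study chair or co-chair to be told before any dose change. This reduces inconsistent handling, but notification is not a recovery criterion.

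**Being forced off treatment is not established.** A reader might infer that an affected patient can never restart and must leave treatment. The documents do not support that. Table 7 only holds the drug, and a residual grade 1 finding in a patient with none at baseline may still clear. An event that has settled at grade 1 no longer matches the grades listed in 5.2.1, so 5.6.1 can be read as satisfied. Section 7.4.3 follows related events to baseline or until they are permanent and stable, which hints at one meaning of resolution but does not define it for 5.6.1.

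**Conclusion.** The inconsistency is real but limited to the 'Other non-hematological toxicity' row at grade 3 or 4. As printed, it affects events that settle at grade 1 or at a baseline grade of 1 or higher. Under the alternative sign it affects only a baseline grade of 2 or higher. The missing baseline statement in Table 7 and the missing grade for 'resolve' in 5.6.1 stand under either sign. Removal from treatment is one possible reading of 5.6.1, not a stated consequence.

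A reader might also infer a measurable rise in the chance of wrongly stopping a stratum at its first stage. At a true response rate of 25%, the chance of no responses is 0.75^9 = 0.075 among nine patients. It would be 0.75^8 = 0.100 if one of the nine could not respond, and 0.75^7 = 0.133 if two could not. These figures are illustrative only. The documents give no rate of such events and no rule that stopping early counts as a non-response. Section 13.1.2 says only that every treated patient is evaluable, and the stratum 2 endpoint in Section 13.2 has no 24-week time point. The case for a change rests on the conflicting text, not on these numbers.

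**What to change.** Confirm the sign in the grade 3 or 4 line of Table 7 against the source document. Then reconcile Table 7, Section 5.3 and Section 5.6.1 so that together they give:

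- one recovery criterion for these events, or an explicit statement of which section governs when a hold meets the start of a course;
- one statement on whether return to baseline is enough;
- one meaning of 'resolve' for the 14-day limit.

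Which grade applies is for the investigators to decide, and this review takes no position on it. The cost is a wording amendment in three places, with no change to the design, sample size or analysis.

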6.2.1 Criteria for continued treatment after toxicity

The study chair or co-chair must be notified of any dosage modification prior to the implementation of the dose modification.

Dose de-escalations to dose level -1 are permitted. See Appendix D.

All patients who require dose de-escalation from dose level -1 must be taken off treatment.

7 ADVERSE EVENTS: LIST AND REPORTING REQUIREMENTS

Adverse event (AE) monitoring and reporting is a routine part of every clinical trial. The following list of AEs (Section 7.1) and the characteristics of an observed AE (Section 7.2) will determine whether the event requires expedited reporting.

Adverse Events and Potential Risks for Selumetinib are listed below. Investigators may also refer to the most current version of the Selumetinib IB for additional expected AE's.

Adverse events will be managed according to local practice.

Expected Adverse Events

Likely (≥20% of patients)	Less Likely (<20% to 3%)	Rare (<3%)		
 Rashes (all) Rashes (acneiform) Diarrhea Nausea Vomiting Asthenic events Peripheral edema Dyspnoea CK increased 	 Dry skin Stomatitis Dry Mouth Facial edema Pyrexia Blurred vision Increased blood pressure ALT/AST increased 	 Paronychia Hyperphosphatemia Hypoalbuminaemia Reduced LVEF Retinal vein occlusion Central serous retinopathy/ retinal pigment epithelial detachment 		

Grouped Term	MedDRA Preferred Terms			
Rashes (all)	Dermatitis acneiform, Rash, Rash erythematous, Rash exfoliative, Rash macular, Rash papular, Rash maculo-papular, Folliculitis, Acne, Rash pustular, Rash pruritic, Rash follicular, Rash generalised, Rash morbilliform			
Rashes (acneiform)	Dermatitis acneiform, Folliculitis, Acne, Rash pustular			
Diarrhoea	Diarrhoea, Frequent bowel movements			
Stomatitis (oral mucositis)	Stomatitis, Mouth ulceration, Oral mucosa erosion			
Asthenic events	Fatigue, Asthenia			
Facial and/or peripheral oedema	Oedema peripheral, Periorbital oedema, Face oedema, Oedema			
Peripheral oedema	Oedema peripheral, Oedema			
Facial oedema	Periorbital oedema, Face oedema, Eyelid oedema			
Fatigue/asthenia	Fatigue, Asthenia			
Pyrexia	Pyrexia, Body temperature increased			
Dyspnoea	Dyspnoea exertional, Dyspnoea, Dyspnoea at rest			
Increased blood pressure	Hypertension, Blood pressure increased, Diastolic hypertension, Systolic hypertension, Blood pressure systolic increased, Blood pressure diastolic increased			
Increased aspartate aminotransferase or alanine aminotransferase	Alanine aminotransferase increased, Aspartate aminotransferase increased, Hypertransaminaseaemia			
Febrile neutropenic events	Febrile neutropenia, Neutropenic infection			
Neutropenic events	Neutropenia, Neutrophil count decreased			
Retinal vein occlusion	MedDRA SMQ (narrow) Retinal disorders			

Physeal dysplasia

A potential risk of effects on bone was identified from a nonclinical experiment. Based on this, pediatric studies of selumetinib should include bone growth assessment at regular intervals including clinical examination, growth chart monitoring and imaging (Section 10 for schedule). Children who show signs of physeal dysplasia at the time of selumetinib discontinuation should have a follow-up assessment after 30 days to evaluate the potential for reversibility.

